Breathing intervention (AIH or SHAM): Breathing interventions will begin 30 min after caffeine or placebo to approximately coincide with peak plasma caffeine concentrations.³⁰ Participants will don a latex-free, full non-rebreather mask with a custom neoprene head strap while they sit comfortably in a semi-reclined chair. Intermittent gas mixtures will be delivered via automatic adjustment of one-way valves attached to a hypoxia generator [HYP123, Hypoxico Inc., USA].³¹ We will deliver preset air mixtures of $\text{FIO}_2=0.09\pm 0.02$ (hypoxia) or $\text{FIO}_2=0.21\pm 0.02$ (normoxia) for 1.5min at 1 min intervals of room air breathing. The generator will fill reservoir bags attached to a non-rebreathing facemask worn by subjects. Oxygen concentration will be continuously monitored [OM-25RME; Maxtec Inc, USA]. We will take precautions to ensure safety during interventions by monitoring 5-lead electrocardiography (ECG) and recording oxyhemoglobin saturation via pulse oximetry (SpO_2) and heart rate (HR) at 2-second intervals. Respiratory rate (RR) and blood pressure (BP) will be recorded every 5th breathing interval [Dash 4000 Patient Monitor, GE]. We also will record SpO_2 , HR, RR, and BP at the start and end of walking practice and again at the end of each treatment session.

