All data will be managed using REDCap⁶⁵, MS 365 Excel 16.54 (Microsoft, USA), and MATLAB R2020a (Mathworks Inc, USA) and will be analyzed using SPSS[®] Statistics 26 (64-bit edition, IBM, USA). Descriptive statistics, including means, standard deviations and 95% confidence intervals of the within-participant pre-post change for each intervention will be calculated for all measures. The baseline characteristics of the participants will be compared using parametric and non-parametric inferencing.

Hypothesis testing: To evaluate our main hypothesis that caffeine prior to AIH enhances walking recovery, we will perform a linear mixed model with fixed effects at a significance at the p=0.05 level.⁶⁶ Intervention (caffeine+dAIH, caffeine+SHAM, placebo+dAIH) and time (day) will be the fixed main effects, with subject as random effect and walking speed (10MWT) as repeat measures. Differences from BL will be compared between and within interventions at D₅, F₁, and F₂. Bonferroni corrections will be made for multiple comparisons. If distributions are not normal, we will perform comparable nonparametric tests. If baseline measures are significantly different between sessions (interventions), an analysis of co-variance (ANCOVA) will be used to analyze the data. We predict walking speed (10MWT) will be greater after daily caffeine+AIH as compared to after daily placebo+AIH and daily caffeine+SHAM.

Blinding integrity analysis: we plan to rigorously quantify blinding integrity here. We will ask participants and raters to guess the intervention received at the end of each intervention and indicate guess confidence using a Likert scale.^{67,68} We will use a contingency table and Fischer's

DETAILED STUDY PROTOCOL

Exact Test to determine if the probability of correct guessing is different from chance. Using multivariate logistic regressions, we also will assess factors that may influence guessing (i.e., adverse events, perceived effects, and sensorimotor changes). In the event of a medical emergency, we will unblind the PI, study participants, and care provider. We also will notify IRB of treatment allocation during adverse event reporting as necessary.

V. Monitoring

21. Data monitoring

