• Blinding Questionnaire		x	x	x	x	x			
• Weight (kg)	x						x	x	
Safety Outcomes									
• Pain (0-10)	x	x	x	x	x	x	x	x	
• Blood pressure (mmHg)	x	x	x	x	x	x	x	x	
• Heart rate (BPM)	x	x	x	x	x	x	x	x	
• Oxygen saturation (%)	x	x	x	x	x	x	x	x	
• Memory (0-30)	x	x	x	x	x	x	x	x	
Biomarkers									
• CYP1A2 Polymorphism	x								
• Caffeine serum level (mg/L)		x				x			
• Inflammation (CRP)		x			x		x		

IV. Statistical Principles

We plan to use a parametric linear mixed model since this method is sensitive to within subject changes and robust against variability, small sample sizes, and missing/unbalanced data sets as compared to other statistical models.²⁶ If the results do not meet these model assumptions, we will apply alternative non-parametric tests.

16. Level of significance

All applicable statistical tests will be 2-sided and will be performed using a 5% significance level.

17. Adjustment for multiplicity

we do not plan to adjust for multiplicity.

18. Confidence intervals

Statistical comparisons will include 95% (2-sided) confidence intervals (CIs).

19. Adherence and protocol deviations

We will record a deviation (if the even does not significantly affect a participant's rights, safety, or well-being, or trial outcomes), or a violation (if the deviation may potentially significantly impact the completeness, accuracy, and/or reliability of the trial data or that may significantly affect a patient's rights, safety, or well-being). All protocol deviations/violations will be logged, but no formal statistical testing will be performed.

Adverse events will be reported on an IRB-approved electronic Case Report Form (eCRF). Details will include the type of event, date of onset, duration, intensity, causality relationship to the study drug(s), and outcome. If an adverse event should occur, every attempt will be made to obtain as much information as possible about event evaluation and outcome. If a serious adverse event occurs, the treatment will be interrupted or discontinued at the physician investigator's discretion. All protocol deviations will be reported to the PI ([name]) and the IRB.

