We will quantify secondary measures of walking function using the timed up-and-go test (TUG, walking initiation and balance), six-minute walk test (6MWT, walking endurance). These tests capture functional ambulation as well as the ability to initiate walking, exhibit high reliability and construct validity.³⁵ Participants will perform 2 trials each of the TUG at their fastest but comfortable and safe speed with a minimum of 1-minute rest between trials. Average speed across the 2 TUG trials will be used for analyses. Subjects will perform the 6MWT once at their fastest, comfortable walking speed sustainable for 6 minutes. Distances will be recorded at 2 and 6 minutes. Participants will use their least restrictive assistive device during these walking assessments.

27. Analysis methods

We plan to analyze within-participant pre-post changes in walking speed (10MWT) for each intervention. We plan to use a parametric linear mixed model for comparing our outcome measure since this method is sensitive to within subject changes and robust against variability, small sample sizes, and missing/unbalanced data sets as compared to other statistical models.²⁶ If the results do not meet these model assumptions, we will apply alternative non-parametric tests.

All data will be managed using REDCap³⁶, MS 365 Excel 16.54 (Microsoft, USA), and MATLAB R2020a (Mathworks Inc, USA) and will be analyzed using SPSS[®] Statistics 26 (64-bit edition, IBM, USA). Descriptive statistics, including means, standard deviations and 95% confidence intervals of the within-participant pre-post change for each intervention will be calculated for all measures. The baseline characteristics of the participants will be compared using parametric and non-parametric inferencing.

Hypothesis testing: To evaluate our main hypothesis that caffeine prior to AIH enhances walking recovery, we will perform a linear mixed model with fixed effects at a significance at the p=0.05 level.³⁷ Intervention (caffeine+dAIH, caffeine+SHAM, placebo+dAIH) and time (day) will be the fixed main effects, with subject as random effect and walking speed (10MWT) as repeat measures. Differences from BL will be compared between and within interventions at D₅, F₁, and F₂.

Bonferroni corrections will be made for multiple comparisons.

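### Within-intervention tests of change from baseline are listed as evidence for the main hypothesis, but only the between-intervention comparison, already planned beside them, can show that caffeine adds to AIH

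*Combined protocol and SAP*

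**What the plan says.** The hypothesis-testing paragraph is the same in SAP 27 (Analysis methods) and Protocol 20 (Statistical methods): "Differences from BL will be compared between and within interventions", at D5, F1 and F2. SAP 27 opens with a further sentence: "We plan to analyze within-participant pre-post changes in walking speed (10MWT) for each intervention". Both sections separately promise means, SDs and 95% confidence intervals of each pre-post change as descriptive statistics.

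The model is described as follows: "Intervention (caffeine+dAIH, caffeine+SHAM, placebo+dAIH) and time (day) will be the fixed main effects". No intervention-by-time term is listed. The protocol, but not the SAP, adds a prediction: "We predict walking speed (10MWT) will be greater after daily caffeine+AIH as compared to after daily placebo+AIH and daily caffeine+SHAM".

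SAP 16 sets the level: "All applicable statistical tests will be 2-sided and will be performed using a 5% significance level". On multiplicity, SAP 17 says "we do not plan to adjust for multiplicity", while SAP 27 and Protocol 20 call for Bonferroni corrections without defining the family.

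Protocol 11a, in the paragraph covering both AIH and SHAM, schedules vital signs "at the start and end of walking practice". The amount of practice is not stated. SAP 26 has the 10MWT measured at BL, D5, F1 and F2, so a participant who completes three interventions is assessed 3 × 4 = 12 times. There is no placebo+SHAM period.

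**The concern.** The question is whether caffeine enhances the effect of AIH. The change from BL within caffeine+AIH is the sum of any caffeine effect, any AIH effect, and whatever walking practice and repeated testing produce. A test of that sum against zero does not isolate the caffeine part. Without a placebo+SHAM period, the trial also has no direct estimate of what practice and retesting do alone.

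The trial's own rationale expects AIH to improve walking without caffeine. A common improvement in both AIH periods is therefore what one should expect if caffeine does nothing. In that situation two within-intervention tests can fall on opposite sides of the significance threshold by chance, and the pair can be mistaken for enhancement. Because the within tests sit under the main-hypothesis heading and no deciding comparison is named, the plan does not close off that reading.

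There is a second, smaller cost. If the Bonferroni family includes the within tests, they use up significance level that the informative comparisons need.

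**Working it through.** **No planned figure to reproduce.** The documents give no error rate for this pattern. The power statement in SAP 11 supplies neither the size of a shared gain nor the correlation of change scores between interventions. Both are assumptions below and are varied.

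**Inputs from the documents.** N=20 recruited, with 17% attrition, so 20 × 0.83 = 16.6 completers (SAP 11). Two-sided 5% level (SAP 16). Three interventions and three post-baseline visits (SAP 27).

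**Step 1: one within test.** Let the true shared gain be d, in SDs of the change score, and let caffeine add nothing. A paired t-test is significant for improvement with probability p = P(T > t_crit), where T is noncentral t with n−1 degrees of freedom and noncentrality d√n.

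**Step 2: the discordant pair at one visit.** With independent change scores, the probability that caffeine+AIH is significant and placebo+AIH is not is p(1−p). This cannot exceed 0.25, reached at p = 0.5. For n=20 at the 5% level:

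| Shared gain d | p | p(1−p) |
|---|---|---|
| 0 | 0.025 | 0.024 |
| 0.2 SD | 0.133 | 0.12 |
| 0.5 SD | 0.564 | 0.25 |
| 0.8 SD | 0.924 | 0.07 |
| 1.0 SD | 0.989 | 0.01 |

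With n=16 the peak is again 0.25 (p = 0.465 at 0.5 SD).

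**Step 3: correlated changes.** The same people supply both changes. Simulation at n=20 and d=0.5 SD gives about 0.25, 0.20, 0.17 and 0.13 for correlations of 0, 0.3, 0.5 and 0.7.

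**Step 4: a stricter threshold.** At d=0.5 SD and n=20, a level of 0.0028 gives 0.13 (correlation 0) or 0.12 (correlation 0.3). The ceiling itself does not fall; its position moves to a larger gain. At 0.0028 and d=0.8 SD, p = 0.567 and p(1−p) = 0.25.

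**Step 5: seconds.** If the 1.3 s in SAP 11 is taken as the SD of the change (an assumption), 0.5 SD is 0.65 s and 1.0 SD is 1.3 s. A shared gain as large as the preliminary-study change of 2.4 s would be 2.4/1.3 = 1.85 SD. Both tests would then almost always be significant, and discordance would be near 0.

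**Step 6: the between contrast.** Under the same null settings, the paired test of the difference in change favours caffeine+AIH in about 2.5% of trials (2.3% to 2.6% across the simulations), whatever the shared gain, because the gain cancels. Discordance together with a significant between contrast occurs in at most 2.3%.

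**Step 7: the comparison family.** Within: 3 interventions × 3 visits = 9. Between: 3 pairs × 3 visits = 9. All 18 give 0.05/18 = 0.0028. The between comparisons alone give 0.05/9 = 0.0056.

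Steps 1 to 4 are per visit. Three visits give more than one chance of discordance, by an amount that depends on the correlation between visits, which is also not given.

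**The case against.** The valid test is already in the plan. The same sentence that lists within comparisons lists between comparisons, and randomised order means that shared practice bears on all interventions alike. Three other places point the same way: the prediction in Protocol 20, the framework in SAP 12, and the sample-size focus on caffeine+dAIH against placebo+dAIH in SAP 11. All of this stands.

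A reader might infer that the plan carries a false-positive rate of 20% to 25%. The documents do not support that. Nowhere do they say that a significant result in one intervention and a non-significant one in another counts as success. The rate belongs to a possible misreading. It is near 25% only when the shared gain puts each within test at about 50% power and the two changes are nearly uncorrelated. No document gives a gain, and the only mention of walking practice is in a vital-signs sentence.

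The 18-comparison Bonferroni family is likewise only one reading, since no family is defined and SAP 17 says there will be no adjustment.

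It can also be said that most of the remedy exists, because descriptive pre-post summaries are already promised. That makes the change cheap. It does not make it unnecessary: the within tests still stand under the main hypothesis, and nothing says they do not decide it.

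**Conclusion.** The concern holds as a matter of specification. Tests that cannot answer the main question are listed as evidence on it, next to the comparison that can, and neither document ranks them. It is not a demonstrated inflation of the trial's type I error.

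The size is conditional. If within-intervention p-values were contrasted, the misleading pattern would arise with no caffeine effect in about 1% to 25% of trials at one visit (n=20, two-sided 5% level, independent changes, shared gain 0 to 1.0 SD). Correlation between changes lowers the figure. A Bonferroni threshold lowers it at a 0.5 SD gain but not at every gain. The between contrast stays at 2.5% in that direction throughout.

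The halving of the threshold from 0.0056 to 0.0028 applies only if Bonferroni is used across all 18 comparisons. SAP 17 and SAP 27 contradict each other on whether it is used at all and must be reconciled.

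**What to change.** In SAP 27 and Protocol 20:

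- Strike the words *and within* from the hypothesis tests.
- Bring SAP 27's opening sentence into line by labelling within-intervention pre-post changes as descriptive: the means, SDs and 95% confidence intervals already planned, without p-values.
- Add a sentence such as: *The main hypothesis is judged only on between-intervention differences in change from BL; caffeine+AIH versus placebo+AIH is the deciding contrast.*
- If BL stays in the model as a repeated measure, add an intervention-by-time term and estimate the contrast through it. With main effects alone, the listed model has no parameter for a difference in change.
- Reconcile SAP 17 with the Bonferroni statement, and define the family if Bonferroni is kept.

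This needs no new data or participants. The cost is a few lines of text in two documents and the loss of within-intervention p-values. Which of D5, F1 and F2 decides is a separate choice that this change does not settle.

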- Concealment mechanism – We will conceal the intervention allocation from the evaluators performing the assessments, treatment administrators, and the study participant.
- Implementation – The PI and biostatistician will generate the allocation sequences for the cross-over study. The trial coordinator will enroll participants and study staff who are not training or assessing the participants will assign the block randomized interventions.

11. Sample size

Twenty individuals with chronic (> 6 months post injury), motor-incomplete SCI (i.e., American Spinal Injury Association Impairment Scale (AIS) C or D) will be recruited for the study. Prior to the start of this clinical trial, we estimated the number of participants needed to achieve study objectives. In particular, our sample size computation focused on treatments: caffeine+dAIH versus placebo+dAIH alone. Our preliminary study on the effects of caffeine prior to single AIH sequence (vs placebo+SHAM) on 10MWT showed a decrease of 2.4s±1.2s. Under the hypothesis of an additive effect of caffeine+dAIH (vs. placebo+dAIH), we anticipate the difference in walking speed (10MWT time) change between treatments would be approximately 0.06m/s. With N=20 cross-over participants (includes 17% attrition rate), a repeated measures ANOVA comparing 4 treatments across 4 time points, using pooled SD of 1.3s across days, will be sensitive to detect a difference at power of $1 - \beta = 0.80$ ($f=0.7$, $F_{3,12}=3.5$; $p=0.4$, $\alpha=.05$).

12. Framework

This placebo-controlled study will examine the combined effects of caffeine and AIH results in greater walking performance than either intervention alone. However, this trial will not evaluate the potential superiority or equivalence of caffeine+AIH to standard of care treatments for persons with chronic iSCI.

13. Statistical interim analyses and stopping guidance

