26. Outcome definitions

The primary outcome measure is change in walking speed (10MWT time, s) relative to baseline (BL). For all analyses, we will use the average of two 10MWT times at BL, D₅, F₁, and F₂. Change

in walking speed will correspond to the difference between post-intervention 10MWT and BL times. Please review Table 1 for timing of outcome assessments.

All the summaries in this section will be equivalent to the main and the final results reports. There will be statistical testing completed for baseline testing of the primary outcome measure (10MWT). Since we plan to use a cross-over study design, we will compare the 10MWT baseline measurements between the interventions to evaluate the effects of the washout period.

Assessment and collection plans: Physical evaluations will be completed by the study's licensed physical therapists or occupational therapists and/or trained research study staff. Functional ability of subjects will be evaluated using standard clinical assessments with high inter-rater reliability: American Spinal Injury Association Impairment Scale (AIS) lower extremity motor scores (LEMS) to quantify strength,²⁸ and Spinal Cord Assessment Tool for Spastic Reflexes (SCATS), and the Penn Spasm Frequency Scale (PSFS) which is a self-report assessment of the frequency and severity of muscle spasms²⁹ and modified Ashworth Scale to quantify spasticity.³⁰ We also will record pain severity using the well-established Wong-Baker FACES scale, which shows high test-retest reliability and interpretability as well as good content and construct validity.^{31,32} Clinical ratings of walking ability, including Walking Index for Spinal Cord Injury (WISCI) II³³ and/or SCI Functional Ambulation Index (SCI-FAI),³⁴ will be assessed based on video recordings of the 10MWT.

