Alternative statistical methods: If distributions are not normal, we will perform comparable nonparametric tests. If baseline measures are significantly different between sessions (interventions), an analysis of co-variance (ANCOVA) will be used to analyze the data.

Blinding integrity analysis: we plan to rigorously quantify blinding integrity here. We will ask participants and raters to guess the intervention received at the end of each intervention and indicate guess confidence using a Likert scale.^{38,39} We will use a contingency table and Fischer's Exact Test to determine if the probability of correct guessing is different from chance. Using multivariate logistic regressions, we also will assess factors that may influence guessing (i.e., adverse events, perceived effects, and sensorimotor changes). In the event of a medical emergency, we will unblind the PI, study participants, and care provider. We also will notify IRB of treatment allocation during adverse event reporting as necessary.

CYP1A2 analysis: we will perform subgroup analysis on our study cohort to determine the extent to which differences in caffeine metabolism due to CYP1A2 polymorphisms may affect responsiveness to the combinatorial treatment of caffeine+AIH.

28. Missing data

Rigorous efforts will be made to ensure complete outcome data. However, we anticipate that participants in this study cohort may be unable to complete the study requirements. Missing data will be reported and documented as we did in our previous clinical trial.⁴⁰ We will document reasons for missing data and our approach to handle missing data during statistical analysis. We will account for potential outliers in our results using a conservative outlier labeling technique set forth by Hoaglin and Tukey.⁴¹

29. Additional analyses

We do not anticipate any additional statistical analyses methods.

30. Harms

Checklists and note pages are used to log any deviations or omissions from the protocols. Any clinical/health related issues would be immediately presented to the subject to determine appropriate notification (i.e., current physician or appropriate specialist). Based on the seriousness of the situation Drs. [name] or [name] may be contacted to provide clinical guidance on the appropriate course of action as per our Laboratory Medical Emergency Safety Plan.

31. Statistical software

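### The rule for replacing the primary mixed model with nonparametric tests is unspecified and worded two ways, so the deciding analysis is settled only after outcome data are seen

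*Combined protocol and SAP*

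**What the plan says.** Protocol 20 and SAP 27 give the same primary analysis: "we will perform a linear mixed model with fixed effects at a significance at the p=0.05 level", with intervention and day as fixed effects and subject as a random effect. Changes from baseline are compared at day 5 and at the two follow-ups.

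Two sentences then allow the model to be replaced:

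- Protocol 20, and SAP 27 under alternative statistical methods: "If distributions are not normal, we will perform comparable nonparametric tests".
- SAP part IV (Statistical Principles), and the opening paragraph of SAP 27: "If the results do not meet these model assumptions, we will apply alternative non-parametric tests".

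The sentence before the second rule, in both places, justifies the mixed model by its robustness with small samples and with missing or unbalanced data.

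SAP 26 defines the endpoint: "The primary outcome measure is change in walking speed (10MWT time, s) relative to baseline (BL". The two test times at each visit are averaged. Protocol 18 says instead that the average speed over the two trials is analysed. Protocol 12 gives the minimum clinically important difference as 0.06 m/s, and SAP 11 uses about 0.06 m/s as the planned difference. On size, SAP 11 states "With N=20 cross-over participants (includes 17% attrition rate". SAP 28 expects that some participants may not complete the study. SAP 18 promises 95% confidence intervals for the comparisons.

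**The concern.** A primary analysis should be identifiable from the plan before anyone sees outcome data. Here it is conditional on a check whose object, method and threshold are left open, and the method that takes over has no name. Two analysts following the plan in good faith could reach different primary tests from the same data.

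The estimand moves with the method. The mixed model estimates a difference in mean change. A rank test addresses a different quantity, and the plan does not say where the promised confidence interval would then come from.

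The switch also works against the SAP's own reason for its choice. Standard rank tests for related samples use only participants with every round the test needs. A mixed model keeps the data of those who are incomplete.

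**Working it through.** **1. The plan's own figure.** SAP 11 gives N=20 and power 0.80, with f=0.7, F(3,12)=3.5 and α=0.05. The documents give no figure for how often the fallback would be used. The stated power is approached only with four independent groups measured four times, reading the printed p=0.4 as a correlation (an assumption):

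- λ = f²·N·m / (1+(m−1)ρ). At N=16, λ = 0.49 × 16 × 4 / 2.2 = 14.3. The critical F(3,12) is 3.49 and power is 0.773. An f of 0.722, which rounds to 0.7, gives 0.80.
- At N=17, λ = 0.49 × 17 × 4 / 2.2 = 15.1 and power is 0.810. Then 17/0.83 = 20.5, so 21 against the stated 20.

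That layout is not the planned three-intervention cross-over. What matters here is the number analysed: 20 × 0.83 = 16.6, so 16 or 17 completers.

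**2. The two triggers side by side.**

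| | Protocol 20; SAP 27, alternative methods | SAP part IV; SAP 27, opening |
|---|---|---|
| Trigger | distributions not normal | model assumptions not met |
| Quantity checked (times, changes, residuals) | not stated | not stated; could be read as residuals |
| Test and threshold | not stated | not stated |
| Replacement test | not named | not named |

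**3. How often the switch would occur.** The documents give no skew, baseline mean or between-participant spread for 10MWT time, so this rests on assumptions: lognormal times, median 21 s (the time at which 2.4 s equals 0.06 m/s), within-participant SD 1.3 s (the pooled SD in SAP 11), n=17, three interventions by four times, and a Shapiro-Wilk test at 5%. The SD is either constant in seconds or proportional to walking time. Monte Carlo error is about 1 point or less.

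| Quantity tested | log-SD 0.3 | 0.5 | 0.7 | 1.0 |
|---|---|---|---|---|
| Raw times, one cell | 20% | 45% | 67% | 88% |
| Changes, one cell, constant error | 5–6% | 5–6% | 5–6% | 5–6% |
| Changes, one cell, proportional error | 10% | 24% | 41% | 66% |
| Residuals (17 × 3 × 4 = 204), constant error | 4–6% | 4–6% | 4–6% | 4–6% |
| Residuals, proportional error | 41% | 84% | 97% | 100% |
| Any of 9 change cells, constant error | 37% | 35% | 36% | 36% |
| Any of 9 change cells, proportional error | 61% | 85% | 96% | 99.5% |

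Nine independent 5% tests on normal data would give 1 − 0.95⁹ = 37%. That explains the sixth row: testing cell by cell often triggers the switch with no skew in the changes at all. Raw times in one cell pass 50% only at a log-SD of about 0.55 (n=17) or 0.50 (n=20).

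**4. Error rates.** For the single contrast of caffeine+AIH with placebo+AIH in day-5 change, choosing between a paired t test and a Wilcoxon test after the normality check gives a type I error of 4.0% to 5.3%. Power for a 1.3 s effect is 48–50% (t) against 45–47% (Wilcoxon) with constant error. With proportional error and log-SD 1.0 it is 25% against 38%.

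**5. Participants dropped.** If attrition means a missing round, a Friedman-type test on all three interventions keeps about 16 or 17 of 20, setting aside the partial data of 20 × 0.17 = 3.4 participants on average. A paired rank test loses only those missing one of its two rounds.

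**6. The scale.** Time is 10/speed. A gain of 0.06 m/s is 10/0.3 − 10/0.36 = 5.6 s for a participant at 0.3 m/s, 10/0.6 − 10/0.66 = 1.5 s at 0.6 m/s, and 10/1.0 − 10/1.06 = 0.6 s at 1.0 m/s. If the effect acts on speed, changes in seconds spread out even when the gains in speed are equal.

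**The case against.** A reader might infer that 10MWT time is skewed and that the switch will therefore be triggered in most trials. Settings that show this can be built. With n=20, median speed 0.6 m/s, a mean gain of 0.06 m/s (SD 0.05) and log-SD of 0.4 to 0.6, normality of the time changes is rejected in 64% to 89% of simulated trials. The documents do not support this as a forecast. Those settings imply a median SD of the time changes of 2.2 to 3.6 s, about 1.7 to 2.8 times the stated 1.3 s. Settings with an SD near 1.2 to 1.4 s (log-SD 0.1 to 0.2) trigger in only 10% to 19%. The documents do not say exactly what the 1.3 s measures, so a low rate is not shown either.

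Other objections also stand:

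- No inflation of type I error was found, and under strong skew with proportional error the rank test has more power.
- The planned mixed model has no term for round, so the switch loses no round adjustment.
- The sized contrast needs two rounds, not three, if a paired test is used.
- N=20 already allows for attrition, so 16 or 17 completers is no unplanned shortfall.
- Rank methods have their own intervals (Hodges-Lehmann).
- One trigger can be read as a residual check.

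None of this says which analysis decides the trial. The width of the range in the table shows how much turns on choices that the plan leaves open.

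**Conclusion.** The point holds as a defect of specification that the plan should repair. The text allows an unnamed test to displace the primary model on an undefined check of outcome data, under two triggers that are not equivalent. This conclusion needs no distributional assumption.

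The frequency of the switch is not determinable: about 5% to nearly 100% under the assumptions above, depending on spread, error structure and the quantity tested. The harm is an undetermined primary analysis and estimand, not a demonstrated excess of false positives; the error-rate check covers one paired contrast only. The loss of incomplete participants is a secondary cost. It is about 3 of 20 at the stated attrition if a complete-case test on all three rounds were used, and depends on which test is chosen.

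**What to change.** Amend Protocol 20, SAP part IV and both places in SAP 27 so that the linear mixed model stays primary whatever a normality test shows. Delete the two switching sentences. Check residuals graphically and report what is seen.

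Fit the model to 10MWT speed in m/s and amend SAP 26 to match. This is the scale of the 0.06 m/s important difference, of the planned difference, and of the averaging rule in Protocol 18.

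Name one within-participant permutation or rank test as a sensitivity analysis, and report the analysis in seconds as another.

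This needs no new data. The cost is not nil, because the estimand moves from seconds to m/s. In a simulation at n=17 with effects acting on speed (log-SD 0.3 to 0.6, assumed), power was about 0.90 to 0.92 on speed against 0.79 to 0.84 for the switching rule applied to time. When effects were constant in seconds, the speed analysis lost power. The team should make that choice before unblinding and record the reason.
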